This study is designed as a randomized control trial. Figure 1 shows the time line for the study. There will be four groups of subjects, (1) normal weight-bearing with massage (WB-M), (2) normal weight bearing without massage (WB-C) (3) ULLS, no massage (control, U-C), and (4) ULLS with massage (U-M). We expect to recruit 140 subjects to in order in fully enroll 128 (32 per group, n = 3 per group for attrition). For measurement of protein synthesis, participants will ingest three 50 mL doses of heavy water (2H2O) for the first two days and the dose will decrease to two 50 mL doses per day (a total of 1000 mL of heavy water for each subject over the course of the trial). 3-4 blood draws will be taken on days 2, 5, 7, and 9 and each will be drawn at the same time each day. Subjects in U-C and U-M groups will have their left leg immobilized and suspended using a hinged knee brace. Those immobilized will be required to wear the brace and use crutches at all times, except while showering and sleeping. Immobilization will begin on day 2 and will continue until the end of the study (day 9). Members of the research team will use a custom-made device to massage the quadriceps region of subjects' left leg and leave the right leg unaffected in the WB-M and U-M groups. Massage treatments will begin on day 3 and will take place every other day (day 5, 7, 9) until the end of the study. A baseline muscle biopsy of the vastus lateralis will be taken from the right leg on day 2, prior to the first massage. Muscle biopsies will then be taken from both legs 4-6 hours after the last massage on day 9, and the muscle tissue will be frozen for further examination. (See Figure 1). Sham treatment for the WB-C and U-C groups will include us touching the skin using a light brushing technique.

For the weight bearing groups as comparison groups, they will also have to drink deuterium oxide heavy water over 9 days which is associated with 3-4 blood draws but will not have to wear a brace or use crutches. Weight bearing control groups will only have one biopsy taken on day 9 while weight bearing massage groups will have two biopsies taken (day 2- right leg, and day 9- left massaged leg). This will still allow for effective comparison between groups and will reduce burden on these participants. We will enroll the weight bearing groups after immobilization groups to ensure that those interested in the study will not drop out after possible randomization into the immobilization group.

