Deuterium oxide heavy water ($2H_2O$) is a stable, non-radioactive isotope that is indistinguishable from normal water. It is simply water that has a higher amount of a natural, but less abundant, form of hydrogen. Subjects will be required to ingest the heavy water for 9 days. (99% D_2O , Cambridge Isotope Laboratories). A target of 1-2% enrichment is achieved during a one week priming stage and maintained for the remainder of the study. Subjects will be sent home with 50 mL doses of heavy water in sealed sterile vials. The first two days, they will consume one 50 mL vial of the heavy water three times a day (150mL/day). The next 7 days, they will consume one 50 mL vial twice a day (100mL/day). This will total 1000mL of water per subject. Over the course of the 9 day trial, the subjects' blood will be drawn on day 2, 5, 7, and 9.

Blood Draws:

Blood samples will be obtained for protein synthesis measures and for the assessment of exosomes and circulating miRNAs. Left over blood will be stored in the lab indefinitely. Approximately 5-25 ml will be drawn.

Immobilization:

Participants of the immobilization/massage and immobilization/no massage groups will be placed in a knee immobilizer on their left leg and crutches, and will be non-weight-bearing starting on day 2 (after the first two days of heavy water intake) of the 9 day trial for a total of 7 days. The participants will be required to log and explain on the attached Immobilization Time Log any time they did not use/wear the crutches or knee immobilizer in order to track compliance.

Massage:

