Subjects will report to the Human Performance Lab, in room B04A of the Multidisciplinary Science building. A custom-made cyclic compressive loading (CCL) device will be used to apply a mechanical load to the left thigh starting on day 3. The knee immobilizer will be removed, and the subjects will be positioned right lateral recumbent with their left hip and leg slightly flexed and the left leg supported by a wedge to maintain anatomical position in the frontal plane. The CCL device will be a commercially available massage roller instrumented with a strain gage to measure applied load. Massage application using a 35 newton load will be applied for 15 minutes every other day over the course of 7 days (days 3, 5, 7, and 9). The CCL device will be placed 10cm proximal to the superior pole of the patella over the vastus lateralis muscle of the left leg, and a normal force of 35N will be applied while rolling the device proximally along the length of the vastus lateralis at a rate equal to one muscle length over 2 seconds. Without interruption, the direction of the massage will then be reversed and the same load and loading rate will be applied proximal to distal. Thus, one complete cycle of massage to the vastus lateralis will take 4 seconds, corresponding to a duty cycle of 0.25Hz. Massage will continue for 15 minutes, resulting in approximately 225 complete cycles. Sham treatment (WB-C and U-C) groups will receive a light touching on the skin using a light brushing technique.

We have previously shown that the beneficial effects of massage can be optimized by application of the appropriate dose¹², including considerations for timing of massage application¹³, duration of massage¹⁴ and the magnitude of applied load.^{5,12} Therefore, we have used allometric scaling laws to calculate optimal loads based on our early investigations demonstrating effectiveness of massage for limiting inflammation and accelerating recovery after injury in rabbit skeletal muscle.¹⁵ We have used this method to successfully scale the optimized loads to rats⁵ and have applied the same methods to calculate the appropriate loads for human massage. We have determined that the optimal load for human vastus lateralis is a normal force of 35N.

Muscle Biopsies:

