On day 2 of the study (after the first two days of heavy water intake), a baseline muscle biopsy will be taken from the vastus lateralis muscle of the right leg. Subjects will be instructed not to eat or drink anything for breakfast the last day of the study when they come in for the last massage and the biopsies. Subjects will be provided a light breakfast consisting of a choice of bagel with cream cheese or

granola bar or muffin with banana and orange juice. Four hours after the last bout of massage one muscle biopsy will be taken from the left and the right vastus lateralis each. Biopsies (100-300 mg tissue) will be taken by one of the two physicians on the study or the physician assistants listed in the protocol. The tissue will be frozen for analysis by the experimenters. In exercise literature a waiting period of about 2-6 hours is what is shown to demonstrate changes in the expression of genes associated with muscle size regulation.^{16,17} In an effort to respect the subjects' time, a waiting period of 4-6 hours was decided. The subjects are allowed to walk around after the massaging, but are asked to refrain from exercising for the 4 hours in between the massage treatment and the muscle biopsy.

Muscle Biopsy Procedure:

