## Statistical Design and Power

Statistical Analysis. The College of Health Sciences supports the effort of a biostatistician through the Office of Research to provide dedicated support to funded investigators. All statistical analyses will be performed using SAS© 9.4 (SAS institute, Cary NC). The sample size calculations herein have been performed with the assistance of the biostatistician. We used 4 main outcomes to determine sample size: cross sectional area (CSA), myofibrillar protein synthesis (MyoKsyn), extracellular vesicle (EV) number and mRNA levels of Rab27. These outcomes were also measured in the pilot study we performed with 6 subjects and the variance and expected differences were based on the data from the pilot study. See Table below.

% change	EV number	CSA	MyoKsyn	Rab27 mRNA
Pilot study data	0.29	6.1	36	116
Expected μ₁-μ₂	0.29	10	70	150
Standard Deviation, σ	0.294	11	76	170
Effect Size, $\delta =  \mu_1 - \mu_2 /\sigma$	0.99	0.91	0.92	0.88
n per Group	18	21	19	22

From this sample size analysis we decided to use n=22 per group, because it would give us the power to determine differences in the mRNA expression of EV biogenesis markers as well as enough power to detect changes in muscle size and protein synthesis. To determine statistically significant differences between the groups we will use a Two Way ANOVA to determine effects of ULLS and massage. Holm Sidak posthoc tests will be performed in case significance is seen with the ANOVA. We will use an unpaired t-test to test for cross over effect (UM versus UC left nonmassaged limb).

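### The SAP's one explicitly defined cross-over test names a left non-massaged limb, which the massaged suspension group (U-M) does not have; the limb should be named for both groups

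*SAP*

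**What the plan says.** SAP, Statistical Design and Power, gives the cross-over analysis in its last sentence: "We will use an unpaired t-test to test for cross over effect (UM versus UC left nonmassaged limb". Neither document defines the test or its limb anywhere else.

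The protocol is consistent about laterality:

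- **Massage.** Under Study Design, staff massage the subject's "left leg and leave the right leg unaffected in the WB-M and U-M groups". Under Research Procedures, Massage, the device "will be used to apply a mechanical load to the left thigh starting on day 3".
- **Suspension.** Under Study Design: "Subjects in U-C and U-M groups will have their left leg immobilized and suspended using a hinged knee brace". Under Research Procedures, Immobilization, both immobilisation groups "will be placed in a knee immobilizer on their left leg and crutches".
- **Tissue.** Study Design plans a baseline sample: "A baseline muscle biopsy of the vastus lateralis will be taken from the right leg on day 2, prior to the first massage". It then plans the final samples: "Muscle biopsies will then be taken from both legs 4-6 hours after the last massage on day 9". Research Procedures, Muscle Biopsies, agrees that on the last day "one muscle biopsy will be taken from the left and the right vastus lateralis each". Only the weight-bearing groups are given a reduced biopsy schedule.

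The Objectives section includes the crossover effect and the possible part played in it by extracellular vesicles. It names no limb.

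**The concern.** A cross-over effect of massage is a response in the limb that was not massaged. In U-M that is the right leg, and the SAP says left. The sentence is the only explicit definition of the test, so no second statement settles the matter.

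The error could also pass unnoticed. A left, non-massaged limb does exist in U-C, so an analyst could take the U-C limb literally, choose a U-M limb by judgement, and obtain a result without any warning. The possible choices answer different questions, and the choice should not be made after the data are seen. The weight-bearing groups offer no substitute at muscle level, because under Study Design WB-M has no right-leg biopsy on day 9.

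**Working it through.** **Step 1. Classify the four limbs.** Inputs are Study Design, Immobilization and Massage in the protocol. U-C receives only a sham, so neither of its legs is massaged.

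| Limb | Massaged | Suspended | Left and non-massaged | Right and non-massaged |
|---|---|---|---|---|
| U-M left | yes | yes | no | no |
| U-M right | no | no | no | yes |
| U-C left | no | yes | yes | no |
| U-C right | no | no | no | yes |

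The SAP's label fits 0 of 2 limbs in U-M and 1 of 2 in U-C. With right in place of left it fits exactly 1 of 2 in each group. This count describes the contradiction; it does not measure its effect on results.

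**Step 2. Try each reading of the sentence.**

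- *Label applies to both groups.* U-M has no such limb, so the test cannot be run.
- *Label applies to U-C only, U-M left used.* Both limbs are suspended and one is massaged. This is the direct effect of massage on the treated limb.
- *Label applies to U-C only, U-M right used.* A limb that is not suspended is compared with one that is, so massage exposure and suspension cannot be separated.
- *Right leg in both groups.* Both limbs are non-massaged and not suspended, and the groups differ in whether the other leg was massaged. Of the comparisons listed, only this one isolates a contralateral effect.

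For scale on the third reading: the protocol's Background puts fibre-size loss under short-term suspension at 3 to 8% per week, and Immobilization gives 7 days. If that rate applies here, suspension alone could produce a difference of 3 to 8 percentage points in fibre size. The SAP's expected CSA difference is 10, in a table headed as per cent change, so this is 3/10 = 0.3 to 8/10 = 0.8 of it. This is an illustration only, since the SAP does not say which contrast its figure of 10 refers to.

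**Step 3. Check that the tissue exists.** The general schedule gives each suspended participant a right-leg biopsy on day 2 and biopsies of both legs on day 9, three in all. The Payment section is compatible with this. Taking $15 per draw and four draws, 4 × 15 + 3 × 50 + 100 + 65 = 375, the stated total for the immobilisation groups. This is support and not proof, because the weight-bearing totals fit only if the $15 is paid once: 15 + 50 + 65 = 130 and 15 + 100 + 65 = 180.

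**Step 4. See whether any printed figure depends on the limb.** The SAP gives 18, 21, 19 and 22 per group for EV number, CSA, MyoKsyn and Rab27 mRNA. It states neither alpha nor power, so two-sided 0.05 and 80% are assumed. With the normal approximation, n = 2(1.960 + 0.842)² / δ² = 15.70 / δ²:

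| Outcome | δ | 15.70 / δ² | n, normal | n, t-test | SAP |
|---|---|---|---|---|---|
| EV number | 0.29/0.294 = 0.986 | 16.1 | 17 | 18 | 18 |
| CSA | 10/11 = 0.909 | 19.0 | 19 | 21 | 21 |
| MyoKsyn | 70/76 = 0.921 | 18.5 | 19 | 20 | 19 |
| Rab27 mRNA | 150/170 = 0.882 | 20.2 | 21 | 22 | 22 |

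The t-test column uses the noncentral t distribution. The stated sizes reproduce to within 2, and no limb enters the calculation. At 22 per group, the same unpaired t-test with the table's inputs has power 0.89, 0.84, 0.85 and 0.82. Those values belong to whatever contrast the table describes, which the SAP does not identify.

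**The case against.** The strongest reply is that this is a one-word slip with an obvious correction. The sentence says cross-over and non-massaged, and U-M has only one non-massaged limb, so an analyst holding the protocol would choose the right leg. Much of this stands: right is the most likely intent, and the tissue is planned. It does not fully settle U-C, where both legs are non-massaged and the written word left points to the suspended one.

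A reader might infer three stronger things that the documents do not support.

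- *That the crossover objective has no other analysis.* The t-test is the only explicitly defined cross-over test, but EV number is one of the four main outcomes and bears on the same objective. The Blood Draws section assesses exosomes in blood, and a blood measure has no limb.
- *That the sample size is wrong for this test, or is shown to be right for it.* Neither follows, because the table does not say which limb or contrast its differences and standard deviations describe.
- *That the outcome scale is also in error and should be set as change from the day-2 right-leg sample.* No such defect is evident. The documents do not explain how MyoKsyn is calculated from the biopsies, and the day-2 sample follows only two days of heavy water, so a usable baseline for that outcome is not established.

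**Conclusion.** The contradiction is real and nothing elsewhere in the documents corrects it. As written, the test either cannot be run or, if the label is confined to U-C, compares limbs that do not isolate a cross-over effect. It affects one sentence and the one explicitly defined cross-over test, changes no printed figure, and should be corrected before analysis.

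The conclusion rests on the protocol's laterality, which is the same in Study Design, Immobilization and Massage, and on the both-leg day-9 biopsy applying to the two suspension groups, as the general schedule implies. That right was intended is an inference for the sponsor to confirm. No power can be claimed for the corrected test from the present table.

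**What to change.** Reconcile the SAP sentence with the protocol's Study Design, Immobilization and Massage sections by naming the limb in both groups. The sponsor should confirm which limb was meant. If it is the right, the sentence could read:

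> Cross-over effect, for biopsy (limb-specific) outcomes: unpaired t-test, U-M versus U-C, right (contralateral, non-massaged, non-immobilised) vastus lateralis.

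The restriction to biopsy outcomes keeps blood-based vesicle measures out of a comparison that is defined by limb.

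The cost is one sentence in the SAP. Right-leg biopsies on day 9 are already planned in both suspension groups, so no new samples or visits are needed and no printed figure has to be revised.
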